6.1 Study Endpoints

6.1.1 Primary endpoints

- 1) Incidence of ARs within 0–28 days after booster immunization.
- 2) Geometric mean titer (GMT) of anti-SARS-CoV-2 specific neutralizing antibodies against omicron BA.4/5 in subjects in the immunogenicity group at 28 days after booster immunization.

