7.3 Exclusion Criteria

- 1) Subjects with a history or family history of convulsions, epilepsy, encephalopathy, or mental disorders;
- 2) Subjects who are allergic to any ingredient of the investigational vaccine, or subjects with a history of severe anaphylactic reactions to vaccines, allergies, or asthma;
- 3) Those with a history of severe vaccine-related ARs following immunization with a vaccine;
- 4) Females who tested positive for urine pregnancy test;
- 5) Subjects with acute febrile disorders, infectious disease, or a history of SARS;
- 6) Axillary temperature > 37.0 °C;
- 7) Subjects with serious cardiovascular diseases, such as arrhythmia, heart block, myocardial infarction, and serious, uncontrolled hypertension despite antihypertensive drugs (on-site measurement: SBP ≥ 180 mmHg and DBP ≥ 110 mmHg);
- 8) Subjects with serious chronic diseases or progressive diseases that cannot be controlled, such as diabetes or thyroid disorders;
- 9) Subjects with congenital or acquired angioedema/neurogenic edema;
- 10) Subjects with a history of urticaria within 1 year prior to receiving the investigational vaccine;

- 11) Subjects with asplenia or functional asplenia;
- 12) Subjects with lung function abnormalities such as chronic obstructive pulmonary disease or pulmonary fibrosis;
- 13) Subjects with a history of COVID-19 infection/disease;
- 14) Subjects with epidemiological exposure to SARS-CoV-2, or travel history to areas of moderate/high risk or abroad within the past 21 days;
- 15) Those who are judged by the investigator with any contradiction to the study protocol or the signing of informed consent being affected due to various medical, psychological, social, or other conditions.

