Skin and mucosal abnormalities	Erythema/pruritus/color changes	Diffuse skin rash/rash maculopapular/dryness/desquamation	Blister/exudation/desquamation/ulceration	Dermatitis exfoliative involving mucosa, erythema multiforme, or suspected Stevens-Johnsons syndrome
Acute anaphylactic reactions**	Local urticaria (blister), not requiring treatment	Local urticaria requiring treatment, or mild angioedema not requiring treatment	Extensive urticaria or angioedema requiring treatment, or mild bronchospasm	Anaphylactic shock, or life-threatening bronchospasm, or laryngeal edema

Symptoms/Signs of organs/systems	Grade 1	Grade 2	Grade 3	Grade 4
Syncope	Near syncope, without loss of consciousness (e.g., presyncope)	Loss of consciousness, not requiring treatment	Loss of consciousness, requiring treatment or hospitalization	NA
Constipation*	Requiring stool softeners and diet adjustment	Requiring laxatives	Obstipation, requiring manual bowel movement or enema	Toxic megacolon or bowel obstruction
Dysphagia	Mild discomfort when swallowing	Restricted diet	Great limitations in eating and talking; unable to consume solid food	Unable to consume liquid food; requiring intravenous nutrition
Arthritis	Mild pain, with inflammation, erythema, or joint swelling; but not interfering with functions	Moderate pain, with inflammation, erythema, or swelling of the joints; interfering with functions, but not affecting daily activities	Severe pain, with inflammation, erythema, or swelling of the joints; affecting daily activities	Permanent and/or disabling joint injuries
New-onset convulsion	NA	NA	1–3 convulsion(s)	Prolonged and multiple convulsions (e.g., status epilepticus) or uncontrollable convulsions (e.g., refractory epilepsy)
Acute bronchospasm	Transient, not requiring treatment; FEV ₁ %: 70%–80%	Requiring treatment: return to normal after treatment with bronchodilators; FEV ₁ %: 50%–70%	Unable to return to normal after treatment with bronchodilators; FEV ₁ %: 25%–50%, or persistent intercostal retraction	Cyanosis, FEV ₁ %: < 25%, or requiring intubation
Dyspnea	Dyspnea during exercise	Dyspnea during normal activities	Dyspnea at rest	Dyspnea, requiring oxygen therapy, hospitalization, or assisted breathing
Insomnia*	Slight sleep problem, not affecting or slightly affecting daily activities	Moderate sleep problem, affecting daily activities	Severe sleep problem, seriously affecting daily activities and requiring treatment or hospitalization	NA

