Irritation or suppression	Mild irritation or mild suppression	Irritability or lethargy	Inability to be soothed or poor response	NA

Symptoms/Signs of organs/systems	Grade 1	Grade 2	Grade 3	Grade 4
Mental disorders (including anxiety, depression, mania, and confusion), for which the detailed symptoms should be reported	Mild symptoms, not requiring medical consultation, or the act not affecting or slightly affecting daily activities	Presence of clinical symptoms, requiring medical consultation, or the act affecting daily activities	Requiring hospitalization, or behavioral ability not supporting the daily life	Tending to harm oneself or other people, or acute mental confusion, or loss of ability for basic self-care
Pain at non-injection sites# (sites should be identified when reporting)	Slight pain, not affecting or slightly affecting daily activities	Pain, affecting daily activities	Pain, causing inability to perform daily activities	Disabling pain, leading to loss of basic self-care ability
Fever※ [axillary temperature (°C)]	37.3 to < 38.0	38.0 to < 38.5	38.5 to < 39.5	≥ 39.5, lasting ≥ 3 days

Notes: FEV₁% = Forced expiratory volume in one second (FEV₁)/Forced vital capacity (FVC)

* Changes in constipation and insomnia before and after vaccination should be noted.

** Type I hypersensitivity.

Pain at non-injection sites other than muscle pain, arthralgia, and headache.

※ Generally, the axillary temperature is used in China and converted to the oral temperature and rectal temperature as necessary. Generally, oral temperature = Axillary temperature + 0.2 °C; rectal temperature = axillary temperature + (0.3–0.5 °C). In the case of persistent hyperpyrexia, its cause should be identified where possible.

Local AEs are all solicited events. Among the above non-injection site (systemic) AEs, solicited AEs include sore throat (considered a systemic AE in the case of intramuscular injection), fever, diarrhea, fatigue, asthenia, nausea, anorexia, vomiting, headache, cough, arthralgia, chest pain, muscle pain at non-injection sites, pruritus at non-injection sites (without skin damage), skin and mucosal abnormalities, rhinorrhea, and sneezing, while the rest are unsolicited AEs. Refer to the Investigator's Brochure for other non-solicited AEs.

General rules for grading of other AEs:

For clinical abnormalities not described in the grading tables above, the severity grading and assessment for AEs are conducted according to the following criteria:

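### Dyspnea is left off the solicited list for an inhaled vaccine, so mild or later breathlessness is ascertained less well than the airway symptoms that are prompted

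*Protocol*

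**What the plan says.** Section 8.7.2 of the protocol divides adverse events into solicited and unsolicited.

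- **Local events.** "Local AEs are all solicited events". For the inhaled vaccine, Table 8.7-1 defines these as dry mouth, hoarseness, oral mucositis, throat swelling and pharyngalgia.
- **Systemic events.** A named list is solicited. It includes "headache, cough, arthralgia, chest pain, muscle pain at non-injection sites" and ends with "skin and mucosal abnormalities, rhinorrhea, and sneezing, while the rest are unsolicited AEs".
- **Dyspnea.** It has its own row in Table 8.7-3, graded by exertion: Grade 1 is "Dyspnea during exercise" and Grade 2 is "Dyspnea during normal activities". It is not on the solicited list.
- **Acute bronchospasm.** It is also graded in Table 8.7-3 and also unsolicited. Every grade carries an FEV1% range. Grade 3, for example, combines such a range with "Unable to return to normal after treatment with bronchodilators".

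The first primary endpoint in section 6.1.1 is "Incidence of ARs within 0–28 days after booster immunization". It is not restricted to solicited events.

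**The concern.** Section 8.6.2 has the subject take a deep breath, inhale until the mist is gone and hold the breath for 5 seconds. The local table for this route stops at the throat, so any symptom below it depends on the systemic list. That list prompts for sneezing, rhinorrhea and anorexia but not for shortness of breath. Elsewhere the protocol does attend to the lungs: section 7.3 excludes "Subjects with lung function abnormalities such as chronic obstructive pulmonary disease or pulmonary fibrosis".

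The first primary objective is safety, and the group of about 10,000 is sized to see uncommon reactions. A transient, non-serious symptom that no item asks about is more easily forgotten or left unmentioned than one with its own diary line. Such events would count towards the primary endpoint if judged related. They would also inform the safety reviews planned at about 2,000 and 5,000 subjects.

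**Working it through.** **1. Is dyspnea prompted?** The solicited systemic list in 8.7.2 was compared with the rows of Table 8.7-3. Dyspnea and acute bronchospasm are in the table but not on the list, and the closing clause makes them unsolicited. The diary card itself is not in the protocol, so what it asks is inferred from this list.

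**2. What other capture exists?**

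| Period | Route | Place in protocol |
|---|---|---|
| First 30 minutes | On-site observation of every subject, with local and systemic responses recorded | 8.7.1 |
| Days 0–14 | Investigator checks each subject for reactions; diary card | 8.7.1 |
| Days 15–28 | Spontaneous reports and regular follow-up | 8.7.1 |
| Days 14 and 28 | Interview of all subjects | 6 |
| Days 0–28 | All adverse events documented, related or not | Table 8.9-1, note e |
| To month 6 | Serious adverse events | 8.7.1, 8.7.6 |

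Immediate or serious airway events should be caught. The checks to day 14 have no stated respiratory content, and Table 8.9-1 schedules a physical examination only at V1 (blood pressure, height, weight, temperature). The exposed part is therefore non-serious breathlessness that is mild or starts after the subject leaves the site.

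**3. The plan's own figure.** Inputs from section 6.2: n = 10,000 and incidence p = 0.0002, with a stated probability of at least 85% of seeing one case.

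P(at least 1) = 1 − (1 − 0.0002)^10000 = 0.8647, or 86.5%. The stated figure reproduces.

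**4. What capture does that figure need?** Let c be the share of true cases recorded. The protocol gives no value, so c is an assumption shown over a range: P = 1 − (1 − 0.0002c)^10000.

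| c (assumed) | P(at least 1 recorded case) |
|---|---|
| 1.00 | 86.5% |
| 0.95 | 85.0% |
| 0.90 | 83.5% |
| 0.75 | 77.7% |
| 0.50 | 63.2% |

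The incidence that gives exactly 85% at full capture is 1 − 0.15^(1/10000) = 0.0001897. Dividing by 0.0002 gives c = 0.948, so the statement holds at about 95% capture or better.

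**5. Effect on the primary incidence, at the sizing incidence only.** Expected cases are 10,000 × 0.0002 = 2. At c = 0.50 one is missed, which is 1/10,000 = 0.01 percentage points. Section 3.4.2 reports 14-day solicited reaction rates of 18.57% and 23.57% in the earlier inhaled groups, so a loss of this size would not be visible in the overall rate. The 0.02% is the protocol's generic sizing value, not an estimate for dyspnea.

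**The case against.** The strongest reply is that nothing here is contradictory or misstated. Section 8.7.2 says its terms rest on reactions seen in earlier trials, on package inserts of similar products and on the national grading guideline. Section 3.4.2 names neither dyspnea nor bronchospasm among the main reactions to the inhaled booster. The oral and throat terms, cough and chest pain are all solicited, and subjects with asthma or chronic lung disease are excluded. This stands as an explanation of the list. It does not show that breathlessness is absent: not being named as a main reaction is not a count of zero. That study had 420 subjects allocated 1:1:1, so 280 received the inhaled product. Even zero cases in 280 would leave a one-sided 95% upper limit of 1 − 0.05^(1/280) = 1.1%.

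A second reply is that soliciting a systemic term does not make it a reaction. Under section 8.7.4 only solicited events at the injection site are related by definition, so dyspnea would still need the investigator's judgment. That is correct. The prompt improves ascertainment; it does not settle causality.

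A reader might infer three stronger points, and the protocol supports none of them.

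- **That airway events reach the primary endpoint only if subjects volunteer them.** The observation period, the checks to day 14, the interviews and the rule to record all adverse events say otherwise. Only part of the day 15–28 collection is spontaneous.
- **That dyspnea and bronchospasm are the harms most specific to the route.** The protocol makes no such judgment and treats the oral and throat terms as the administration-site events.
- **That acute bronchospasm should be solicited in the same way.** Each of its grades includes an FEV1% range, so it cannot be graded from a lay diary without a lung-function test. The dyspnea grades can.

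**Conclusion.** The point holds in a limited form. Leaving dyspnea unsolicited for an orally inhaled vaccine makes ascertainment of non-serious, mild or later breathlessness weaker than for cough, rhinorrhea or sneezing. It does not remove such cases from the trial.

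The effect on the primary reaction rate cannot be computed from the protocol. At the sizing incidence it would be at most about 0.01 percentage points with half the cases missed, so what is at stake is detection of this particular symptom, not the overall rate.

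It would also be wrong to conclude that the detection statement in section 6.2 is in error. It is correct at 86.5% and remains so down to about 95% capture. The lower figures depend entirely on assumed capture rates. The conclusion further assumes that the diary follows the solicited list in section 8.7.2. This is a worthwhile, inexpensive improvement to data collection, not the correction of an error.

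**What to change.** In section 8.7.2, add dyspnea to the solicited systemic events for both arms over days 0–14. Word it on the diary in lay terms such as shortness of breath or wheeze, and grade it with the dyspnea row already in Table 8.7-3. Leave acute bronchospasm as an event diagnosed by the investigator, with no lung-function test added. Section 6.2 needs no change.

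The cost is one sentence in the protocol and one more line on the diary card and the eCRF. The diary becomes slightly longer, and the reported reaction incidence may rise a little because more mild episodes are recorded. The change does not alter collection in days 15–28.

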8.7.3 Outcomes of adverse events

The outcome of AEs include: 1) resolved; 2) resolved with sequelae; 3) improved; 4) ongoing; 5) death; 6) lost to follow-up.

8.7.4 Relationship between adverse events and investigational vaccines

The investigators should try their utmost to explain the AEs and assess its possible causality, i.e., the causality between the investigational vaccination and the alternative causes (e.g., history of underlying diseases and concomitant treatments). This is applicable to all AEs, including serious AEs and non-serious AEs.

Causality assessment will be conducted according to the reasonableness of the explanation of events from one or more perspectives as follows:

- Response of similar nature observed previously in the drug products of the same kind;
- Same event reported in the literature on the drug products of similar kinds;
- Event temporally associated with vaccination of the investigational vaccine and shown again after its re-vaccination.

By definition, all solicited AEs (e.g., all solicitedly reported local AEs) at the injection sites are deemed related to vaccination. The causality between an AE and vaccination should be assessed by investigators according to their judgment on the presence/absence of a reasonable possibility of an AE occurring due to the vaccination:

- Related: A connection is suspected between the investigational vaccine and the AE (the extent of possibility cannot be determined); there is a reasonable possibility that the investigational vaccine leads to the AE.

- Not related: No relationship between the investigational vaccine and the AE is suspected; there are other more possible causes and the investigational vaccination is not suspected to contribute to the AE.

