8.7.2 Contents and parameters of safety observation

Based on the types and incidence of ARs observed in previous clinical trials as well as the ARs listed in the package inserts of similar products available on the market, this study has adhered to the "Guidelines for Grading Criteria of Adverse Reactions in Clinical Trials of Preventive Vaccines" (No. [2019]102 issued by NMPA). The contents and parameter grades of post-vaccination safety observations are presented in Tables 8.7-1 to 8.7-3, and the grading of vital sign-related safety is shown Table 8.7-4.

Table 8.7-1. Grading of administration-site (local) AEs of the nebulized inhalation vaccine

Symptoms/Signs	Grade 1	Grade 2	Grade 3	Grade 4
Dry mouth	Transient, not requiring treatment, and not affecting daily activities	Dry mouth, slightly affecting daily activities	Seriously affecting daily activities and requiring treatment	NA
Hoarseness	Transient, not requiring treatment, and not affecting daily activities	Hoarseness, affecting normal speech	Seriously affecting daily activities and requiring treatment	NA
Mucositis oral	Transient, not requiring treatment, and not affecting daily activities	Slightly affecting daily activities	Seriously affecting daily activities and requiring treatment	NA
Throat swelling	Transient, not requiring treatment, and not affecting daily activities	Throat redness and swelling, slightly affecting swallowing function	Seriously affecting daily activities and requiring treatment	NA
Pharyngalgia	Transient, not requiring treatment, and not affecting daily activities	Pain pharynx, slightly affecting daily activities	Severe pharyngalgia, seriously affecting daily activities, and requiring drug treatment	NA

Table 8.7-2. Grading of injection-site (local) AEs of the intramuscular vaccine

Symptoms/Signs	Grade 1	Grade 2	Grade 3	Grade 4
Pain	Not affecting or slightly affecting limb activities	Affecting limb activities	Affecting daily activities	Leading to loss of basic self-care ability or hospitalization
Induration*, swelling** #	Diameter of 2.5 cm to < 5 cm or area of 6.25 cm ² to < 25 cm ² and not or slightly affecting daily life	Diameter of 5 cm to < 10 cm or area of 25 cm ² to < 100 cm ² or affecting daily life	Diameter ≥ 10 cm, or area ≥ 100 cm ² , or ulceration, secondary infection, phlebitis, aseptic abscess, or wound drainage, or seriously affecting daily activities	Abscess, exfoliative dermatitis, or necrosis of dermal or deep tissues

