Rash* and redness** #	Diameter of 2.5 cm to < 5 cm or area of 6.25 cm ² to < 25 cm ² and not or slightly affecting daily life	Diameter of 5 cm to < 10 cm or area of 25 cm ² to < 100 cm ² or affecting daily life	Diameter ≥ 10 cm, or area ≥ 100 cm ² , or ulceration, secondary infection, phlebitis, aseptic abscess, or wound drainage, or seriously affecting daily activities	Abscess, exfoliative dermatitis, or necrosis of dermal or deep tissues
Pruritus	Pruritus at the injection site, relieved spontaneously or within 48 h after treatment	Pruritus at the injection site, not relieved within 48 h after treatment	Affecting daily activities	NA
Cellulitis	NA	Requiring non-injection treatment (e.g., oral antibacterial, antifungal, and antiviral treatment)	Requiring intravenous injection treatment (e.g., intravenous antibacterial, antifungal, and antiviral treatment)	Sepsis or tissue necrosis, etc.

Notes: * In addition to grading and evaluation by direct measurement of diameter, progress and changes in the measurement results should also be recorded.

** The greatest measured diameter or area should be used.

For the evaluation and grading of induration and swelling, rash, and redness, indicators with greater grades should be selected based on the functional grades and actual measurement results.

Table 8.7-3. Grading of non-injection-site (systemic) AEs (sore throat is a systemic AE in the case of intramuscular injection)

Symptoms/Signs of organs/systems	Grade 1	Grade 2	Grade 3	Grade 4
Diarrhea	Mild or transient, 3–4 times/day, abnormal stool properties, or mild diarrhea for less than 1 week	Moderate or persistent, 5–7 times/day, abnormal stool properties, or diarrhea > 1 week	> 7 times/day, abnormal stool properties, or hemorrhagic diarrhea, orthostatic hypotension, electrolyte imbalance, and requiring intravenous infusion > 2 L	Hypotensive shock, requiring hospitalization
Nausea	Transient (< 24 h) or intermittent, normal food intake	Persistent nausea resulting in decreased food intake (24–48 h)	Persistent nausea resulting in minimal food intake (> 48 h) or rehydration indicated (e.g., IV fluids)	Life-threatening consequences (e.g., hypotensive shock)
Anorexia	Decreased appetite, without reduced food intake	Decreased appetite associated with decreased food intake, without significant weight loss	Decreased appetite, associated with significant weight loss	Intervention indicated (e.g., gastric tube feeding and parenteral nutrition)

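### Section 8.7.4 ties automatic relatedness to injection sites, so which solicited events count as adverse reactions can differ by arm or site, in a direction that depends on the reading

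*Protocol*

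**What the plan says.** The first primary endpoint (section 6.1.1) is "Incidence of ARs within 0–28 days after booster immunization". Section 8.11.4.2.3 compares groups on it by chi-square or Fisher's exact test. Whether an adverse event (AE) becomes an AR depends on section 8.7.4, which has two parts:

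- Automatic: "By definition, all solicited AEs (e.g., all solicitedly reported local AEs) at the injection sites are deemed related to vaccination".
- Judged: "The causality between an AE and vaccination should be assessed by investigators according to their judgment" of whether there is a reasonable possibility that the vaccine caused it.

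Section 8.7.2 names the sites differently by route. Table 8.7-1 is headed "Grading of administration-site (local) AEs of the nebulized inhalation vaccine" and lists dry mouth, hoarseness, oral mucositis, throat swelling and pharyngalgia. Table 8.7-2 is headed "Grading of injection-site (local) AEs of the intramuscular vaccine". The title of Table 8.7-3, for systemic events, adds that "sore throat is a systemic AE in the case of intramuscular injection". The text after the tables says "Local AEs are all solicited events".

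The trial is open-label (section 6). In the immunogenicity group 420 subjects are randomized 1:1, and about 10,000 others receive the inhaled vaccine without a randomized control.

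**The concern.** The automatic rule uses the term that the tables reserve for the intramuscular vaccine, and one arm receives no injection. Investigators who know the allocation apply the rule while data are being collected, so a later analysis cannot recover a relatedness call that was made under a different understanding.

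Two things are at stake. In the randomized part, 210 against 210, AR status could be assigned by rule for some events in one arm and by judgement for the corresponding events in the other. In the whole inhaled population, 10,000 + 210 = 10,210 subjects at six centers that may each set up several vaccination sites (section 6.3.2), different teams could read the sentence differently. AR incidence would then lack a uniform definition even without a comparison. The suspension criteria in section 6.5 also count adverse reactions, so the two sections should rest on one definition.

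**Working it through.** **Step 1. The two readings side by side.** Sore throat and pharyngalgia are taken as the same symptom.

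| Solicited event | Literal reading (injection sites only) | Broad reading (all solicited local events) |
|---|---|---|
| ICV local events, Table 8.7-2 | automatic | automatic |
| Inhalation local events, Table 8.7-1, other than pharyngalgia | judged | automatic |
| Pharyngalgia after inhalation (local) | judged | automatic |
| Pharyngalgia after ICV (systemic) | judged | judged |

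Under the literal reading the asymmetry lies in the local events and can lower the inhaled AR rate relative to ICV. Under the broad reading it lies in pharyngalgia alone and can raise the inhaled rate. The two asymmetries never occur together.

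**Step 2. Inputs for a size.** Section 3.4.2 reports solicited ARs within 14 days in the earlier study: 420 subjects at 1:1:1, so 140 per group. Groups A and B were inhaled at low and high dose; group C was inactivated vaccine.

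| | A | B | C |
|---|---|---|---|
| Any solicited AR | 26 | 33 | 54 |
| Local | 9 | 16 | 45 |
| Systemic | 26 | 27 | 21 |

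**Step 3. Reproduce the stated figures.** 26/140 = 18.57%, 33/140 = 23.57%, 54/140 = 38.57%. Local: 9/140 = 6.43%, 16/140 = 11.43%, 45/140 = 32.14%. Pearson chi-square on 26, 33 and 54 of 140 gives 15.42 on 2 df, P = 0.00045, against the stated 0.0004. All agree.

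**Step 4. Bound under the literal reading.** A subject leaves the any-AR count only if all of that subject's ARs were local. Local-only = any − systemic:

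- A: 26 − 26 = 0
- B: 33 − 27 = 6
- C: 54 − 21 = 33

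Take the extreme in which every inhalation-site local AR is judged unrelated and the ICV events stay automatic:

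- A stays at 26/140 = 18.57%. The gap to C stays at (54 − 26)/140 = 20.0 points (Fisher P = 0.0003).
- B falls from 33/140 = 23.57% to 27/140 = 19.29%, that is 6/140 = 4.3 points. The gap to C widens from (54 − 33)/140 = 15.0 to (54 − 27)/140 = 19.3 points (Fisher P from 0.0096 to 0.0006).

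**Step 5. Local tables.** The local AR rates are more exposed than the overall rate. All of the 6.4% to 11.4% seen with the inhaled doses would be a matter of judgement, while the 32.1% with inactivated vaccine would be fixed by rule.

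**Step 6. Broad reading.** The protocol gives no pharyngalgia counts by arm, so no size can be derived. Only the direction is known.

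**The case against.** The strongest reply is that the broad reading is the sensible one. The sentence offers solicited local events as its own example, section 8.7.2 says local events are all solicited, and Table 8.7-3 equates non-injection-site with systemic. If the term excluded inhalation sites, dry mouth and hoarseness would count as systemic, against Table 8.7-1. This has force: the literal reading cannot be presented as settled. But the words restricting the rule to injection sites remain, and the broad reading still leaves pharyngalgia automatic in one arm and judged in the other.

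The second reply is that the effect is small. Section 8.7.4 counts a similar reaction seen before with products of the same kind as support for causality, and section 3.4.2 names dysphonia, dry mouth, oral mucositis and pharyngeal swelling as main local ARs of the inhaled vaccine. Most such events would probably be judged related anyway. That stands, and makes the bound in step 4 an extreme.

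Third, the incidence of all AEs over 0–28 days is a secondary endpoint (section 6.1.2), summarized by severity and symptom, so an asymmetry would leave a trace. This is partial cover: that endpoint mixes solicited with unsolicited events and does not repair the AR definition.

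Fourth, labelling sore throat by route is stated openly and is reasonable, since the throat is an administration site only for inhalation. This also stands. The primary endpoint counts ARs at any site, so the label alone changes only the local and systemic breakdowns.

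**Conclusion.** The point holds as an ambiguity in a rule that feeds a primary endpoint. Under either reading AR classification can differ by arm, and if sites read the sentence differently it can differ by site as well.

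A reader might infer that the protocol favors the inhaled vaccine and biases the primary AR comparison. The documents do not support that. The direction reverses between the readings, the hypothesis in section 8.11.2 concerns neutralizing antibody only, no safety hypothesis or margin is set, and most inhaled subjects have no randomized control. A reader might also infer from the local rates that a large part of the inhaled AR incidence is at risk. The counts do not show this either: the shift in overall incidence is 0 to 4.3 points, and the inhaled groups stay below the inactivated-vaccine group with or without it.

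That range assumes that the earlier 14-day solicited rates carry over to this trial's 0–28 day endpoint, that relatedness of systemic events is unchanged, and that every inhaled local AR is reclassified. It counts only events already classed as ARs there, so inhalation-site events judged unrelated in that study are not captured.

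**What to change.** 1. In section 8.7.4, replace the reference to injection sites with: *at the administration site (all events in Tables 8.7-1 and 8.7-2)*.
2. State one relatedness rule for solicited pharyngalgia in both arms, either automatic in both or judged in both. The first change alone would leave it automatic after inhalation and judged after ICV. The local or systemic label can stay as it is if comparative tables carry a footnote.
3. Report the incidence of all solicited AEs by arm, regardless of causality, beside the AR incidence.

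The cost is one phrase and one sentence in section 8.7.4, a line in site training so that all centers apply it alike, and one further table from data already collected. The downside is that the reported AR rate of the inhaled vaccine may be slightly higher.
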